4.8 Safety Analyses

All safety analyses will be conducted using the Safety population. Unless otherwise specified, no formal statistical hypothesis testing will be performed for safety endpoints, and the presentations will be based on descriptive summaries.

4.8.1 Adverse Events

Analyses of AEs will be performed for those events that are considered to be treatment-emergent adverse events (TEAEs). A TEAE is defined as any AE that was absent (i.e., had not occurred) prior to the start of study drug and which occurs on or after the date of the first dose of study drug and within 30 days of the last dose of study drug, or any AE that started during the study period(s) prior to the start of study drug and worsened in severity after the start of study drug within 30 days of the last dose of study drug.

In any tabulation of adverse events, a subject contributes only once to the count for a given SOC or PT. For summaries by severity, a subject with multiple occurrences of an AE will be represented under the most severe occurrence. For summaries by relationship to study drug, a

subject with multiple occurrences of an AE will be represented under the most related occurrence.

The number (%) of subjects with TEAEs will be summarized by SOC and PT. This analysis will also be performed for the following types of AEs: most common ($\geq 5\%$) TEAEs, severe TEAEs, serious TEAEs (SAEs), TEAEs leading to study withdrawal, drug-related TEAEs (with probable or possible relationship to study drug), and AEs that are not treatment-emergent.

The number (%) of subjects with TEAEs by SOC and PT will also be tabulated by maximum severity (mild, moderate, or severe). Subjects with multiple occurrences of a single AE will be counted using the most severe AE. A similar tabulation will be presented by relationship (related or not related) to study drug.

TEAEs associated with the below AEs of special interest (AESI) will be summarized:

- Skin AESI
- Hypersensitivity AESI

Subject listings will be provided for all AEs by SOC and PT. Listings will also be produced for AEs with outcome of deaths, severe AEs, SAEs, AEs leading to discontinuation of study drug withdrawal, Skin AESI, Hypersensitivity AESI and unanticipated adverse device effects (UADEs).

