## Follow-up Visit (Day 36)

A follow up visit 7-days following Visit 5/EOT can be done either in clinic or remotely via a phone follow up. Assessment of local tolerance will be conducted for subjects with ongoing signs or symptoms of local skin reactions and a review of AEs and concomitant medications will be done.

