Document AEs a concomitant med			After signing informed consent until follow up visit				
PK draw 				X	X	X	
Serum marker of metabolism (s-Pl	NP) 			X	X	X	
Drug supply / Dr		_		X	X		
Drug Accountab	ility				X	X	

- 1. A complete physical examination includes a review of the following systems: head/neck/thyroid, eyes/ears/nose/throat, respiratory, cardiovascular, lymph nodes, abdomen, skin, musculoskeletal, and neurological. Breast, anorectal, and genital examinations will be performed when medically indicated. After screening, any clinically significant abnormal findings from the symptom-directed physical examinations should be reported as AEs.
- 2. Including alcohol and tobacco use assessment.
- 3. Blood pressure, pulse rate, body temperature, and respiration rate are to be recorded predose at each study visit. Only blood pressure, pulse rate and respiration rate are to be recorded 1 hour after abaloparatide-sMTS application at each study visit during the treatment period. All blood pressure assessments will be orthostatic. Pulse rate will also be obtained at 15 minutes after abaloparatide-sMTS application at Day 1 (Visit 3), Day 15 (Visit 4) and Day 29 (Visit 5/EOT).
- 4. Height is to be measured at the screening visit/ Visit 1 in the standing position using a medical stadiometer.
- 5. During the Treatment Period, ECGs are to be performed predose after 5 minutes of rest and prior to any blood draw, and 1 hour after abaloparatide-sMTS application on Day 1 (Visit 3), Day 15 (Visit 4) and Day 29 (Visit 5/EOT).
- 6. All routine urinalysis will be performed on a sample freshly voided during the visit and sent to a local laboratory for microscopy if test is positive for micro-organisms via dipstick.
- 7. Blood draw for serum chemistry and hematology will be done during the Screening (Visit 1) and at predose on Day 1 (Visit 3), Day 15 (Visit 4) and Day 29 (Visit 5/EOT).
- 8. Blood draw for serum calcium, albumin and phosphorus will be done at predose and at 4 hours after abaloparatide-sMTS application on Day 1 (Visit 3), Day 15 (Visit 4) and Day 29 (Visit 5/EOT).
- 9. Blood draw for cAMP taken predose and at 30 minutes after abaloparatide-sMTS application on Day 1 (Visit 3), Day 15 (Visit 4) and Day 29 (Visit 5/EOT).
- 10. A 24 hour urine collection will start on Day -8 and complete on the day of the pre-treatment visit (Day -7).

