- 11. All subjects will have a urine drug screen for drugs of abuse and alcohol performed on the Screening Period (Visit 1), and on Day 1 (Visit 3).
- 12. When necessary, re-training may be done post Day 1 / Visit 3.
- 13. Study drug is self-administered daily beginning Day 1 (Visit 3) through Day 29 (Visit 5/EOT), inclusive. On Days 1, 15, and 29, subject will self-administer abaloparatide-sMTS at the study site.

- 14. BMD measured by DXA at Screening visit if most recent DXA was done over 12 months prior to screening.
- 15. Investigators will perform an assessment of the application site at each clinic visit prior to application of abaloparatide-sMTS, 5 minutes after application (ie, immediately upon removal of the patch), and 1- hour following abaloparatide-sMTS application. Signs of local skin reactions will be assessed using a 4-point scale, as described in Section 6.6.2.1.
- 16. The subject will maintain a diary to record their assessment of symptoms of local skin reactions for 29 days beginning on Day 1 (Visit 3). The subject will evaluate the application site prior to study drug administration, 5 minutes after application (ie, immediately upon removal of abaloparatide-sMTS), and 1 hour after abaloparatide-sMTS application. Symptoms of local skin reactions will be assessed using a 4-point scale as described in Section 6.6.2.2.
- 17. Subject assessment of patch adhesion immediately prior to abaloparatide-sMTS removal on each day of the treatment period from Day 1 (Visit 3) to Day 29 (Visit 5/EOT).
- 18. An assessment of pain (separate from the pain question on the 4-point scale for local tolerance) will be done after sMTS application.
- 19. The Subject Diary will be reviewed by study personnel at each study visit to ensure subject compliance.
- 20. AEs and SAEs will be recorded on the case report forms starting from the signing of the informed consent until 7 days after the last dose of study medication. All treatment-related AEs will be followed until resolution or stabilization. Any SAEs that occur at any time after completion of the study, which are considered by the investigator to be related to study treatment, must be reported to the Sponsor or its designee.

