## 7.1. Evaluation of Safety

Timely, accurate, and complete reporting and analysis of safety information from clinical studies are crucial for the protection of subjects and is mandated by Regulatory Agencies worldwide. All clinical studies sponsored by RADIUS will be conducted in accordance with Standard Operating Procedures that have been established to conform to regulatory requirements worldwide to ensure appropriate reporting of safety information.

All AEs are collected from the time of signing the informed consent until 7 days after last dose of investigational product. At any time after 7 days from the last dose of study treatment, the investigator may report any SAE that he/she believes is possibly related to study treatment. Where possible, a diagnosis rather than a list of symptoms should be recorded. All AEs should be captured on the appropriate AE pages in the eCRF and in source documents. The Investigator will assess the relationship of all AEs to the study drug.

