#### 7.1.4. Serious Adverse Event Reporting

Any SAEs that occur during the study from the time the subject signs the ICF until 7 days after the last dose of study medication must be reported within 24 hours of first awareness of the event by completing and faxing the SAE Form and entering data in the clinical trial eCRF. In addition, all SAEs including all deaths which occur up to and including 7 days after administration of the last dose of study drug, must be reported to the Medical Monitor within 1 working day. SAE forms will be provided to the clinical study site. The reference safety information for this study is included in the IB, which will be provided under separate cover to all investigators.

Any SAEs that occur at any time after completion of the study, which the Investigator considers to be related to study drug, must be reported to the Sponsor or its designee.

The Investigator must submit the SAE to the IRB in accordance with 21 CFR parts 56 and 312 as well as with applicable local regulations. Documentation of these submissions must be retained in the site study file.

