## 7.1.5. Device Reporting

Abaloparatide-sMTS is a drug-device combination product. In order to fulfil regulatory reporting obligations worldwide the investigator is responsible for the detection and documentation of events meeting the definition of UADEs that occur with abaloparatide-sMTS (Section 7.1.3.1).

Any UADEs that occur during the study with abaloparatide-sMTS from the time the participant signs the ICF until 30 days after the last dose of study medication must be reported within 24 hours of first awareness that the event meets the definition of a reportable incident by entering data in the clinical trial eCRF. Treatment-related UADEs will be followed until resolution or stabilization, the condition is otherwise explained, or until the subject is lost to follow-up.

The investigator will comply with the applicable local regulatory requirements relating to the reporting to the IRB.

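### The SAP counts treatment-emergent AEs to 30 days after the last dose, but routine AE collection stops at 7 days; read literally, its definition also excludes same-severity recurrences of events that resolved before dosing.

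*SAP*

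**What the plan says.** **Analysis window.** On timing, the first limb of the TEAE definition in SAP 4.8.1 requires an event that "occurs on or after the date of the first dose of study drug and within 30 days of the last dose of study drug". On history, this limb takes "any AE that was absent (i.e., had not occurred) prior to the start of study drug". The second limb takes an AE that began before study drug and worsened after its start, with the same 30-day limit.

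**Collection window.** Protocol 7.1 states: "All AEs are collected from the time of signing the informed consent until 7 days after last dose of investigational product". Protocol 7.1.4 requires SAEs to be reported "from the time the subject signs the ICF until 7 days after the last dose of study medication". Footnote 20 to the protocol's schedule (Table 1) has AEs and SAEs recorded "until 7 days after the last dose of study medication", and the SAP reproduces that footnote under its own Table 1. The AE row of the schedule reads "After signing informed consent until follow up visit". The protocol synopsis describes the last planned contact: "A follow up visit 7-days following Visit 5/EOT can be done either in clinic or remotely via a phone follow up".

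**After day 7.** Protocol 7.1 allows the investigator to report a later SAE thought possibly related; protocol 7.1.4 requires related SAEs after study completion to be reported, with no end date. Under protocol 7.1.5, UADEs occurring "until 30 days after the last dose of study medication must be reported within 24 hours" of awareness. Treatment-related AEs already known are followed to resolution or stabilization (protocol 7.1.6), and local skin reactions ongoing at Day 29 continue to be assessed (protocol 6.6.2.1).

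**The concern.** A TEAE table is normally read as the incidence of new or worsened events over the stated window, with all events in that window sought in the same way. Here they are not. Up to 7 days after the last dose, every AE is collected whatever its cause or seriousness. From day 8 to day 30 a new event reaches the database only if it is serious and judged related, or is a device effect within the UADE definition. An event already under follow-up as treatment-related can also worsen. SAP 4.8.1 tabulates TEAEs by relationship, severity and seriousness, which are largely the properties that decide whether a late event is seen at all.

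The definition raises a second question. AEs are recorded from consent, and screening can begin on Day -67. A headache that occurred and resolved in screening and then returned on drug, no worse than before, fails the first limb on a literal reading because it had occurred. It fails the second because it did not worsen. An on-drug event would then sit outside the TEAE count.

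**Working it through.** **Inputs**
- Last planned dose: Day 29 (Table 1, footnote 13).
- Routine collection: 7 days after last dose (protocol 7.1; footnote 20 in both documents).
- TEAE window: 30 days after last dose (SAP 4.8.1).
- Clinic visit windows: ±2 days (Table 1).
- Planned number treated: about 22 (protocol synopsis).

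**Reproducing the plan's figure.** Day 29 + 7 = Day 36, the stated day of the follow-up visit.

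**The gap.** The TEAE window ends on Day 29 + 30 = Day 59. Days without routine collection: 59 − 36 = 23, that is, post-dose days 8 to 30. This is 23/30 = 77% of the post-dose part of the window. A subject who stops early has the same 23-day gap, because both limits run from the last dose.

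**Do visit windows close it?** If the windows apply independently, Visit 5 falls on Days 27 to 31 and Visit 6 on Days 34 to 38. With the last dose at Visit 5, the final contact comes between 34 − 31 = 3 and 38 − 27 = 11 days after it. Even at 11 days, 30 − 11 = 19 days remain with no planned contact.

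**What can enter on post-dose days 8 to 30**

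| Event | Provided for? |
|---|---|
| New non-serious AE, not a UADE | No |
| SAE judged unrelated, not a UADE | No |
| SAE judged related | Yes (7.1, 7.1.4) |
| UADE | Yes, to day 30 (7.1.5) |
| Worsening of a followed treatment-related AE or ongoing skin reaction | Yes (7.1.6, 6.6.2.1) |

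**Does another passage justify 30 days?** Protocol 8.4.4 calls for TEAE summaries but gives no window. SAP Section 5 names only the Bone Metabolism Population as a change and calls the rest enhancements. The concomitant-medication summary in SAP 4.4 stops 1 week after the last dose. None supports 30 days for AEs in general.

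**Recurrence, on the literal reading**

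| Pre-dose event that resolved, then on drug | Limb 1 | Limb 2 | TEAE? |
|---|---|---|---|
| Recurs, worse | Fails | Can be read as met | Yes |
| Recurs, same or lower severity | Fails | Fails | No |

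**Scale.** One subject in 22 is 1/22 = 4.5%. That is the step size of any table row, not an estimate of the defect. The ≥5% table needs 0.05 × 22 = 1.1, so 2 subjects.

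**The case against.** The strongest reply is that the effect may be nil. Late entry needs a related SAE, a UADE or a worsening of a followed event, and over 23 days in about 22 women there may be none. Safety is descriptive with no comparator, so no test or treatment contrast can be biased. The SAP prints the 7-day collection rule, so a careful reader could see the mismatch. A wider window also has a merit: it keeps a late related SAE in the main table. All of this stands, and it limits the importance of the point. It does not remove the mismatch between what the table claims to count and what the trial collects.

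On recurrence, protocol 7.1.3 treats events as records with their own onset and stop dates. Read per record, a new on-drug headache had not occurred before dosing and meets the first limb. The reading is possible, but the SAP does not say that it applies, and it leaves the parenthesis in the definition with little to do. The wording is ambiguous rather than plainly wrong.

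Three stronger inferences are tempting and not supported:
- **That nothing is collected in those 23 days.** Routine collection stops; related SAEs, UADEs and followed events are still covered.
- **That the 7-day SAE and 30-day UADE windows contradict each other.** The 7-day limit applies to SAEs whatever their cause. Related SAEs have no end date (protocol 7.1.4), and the UADE definition in protocol 7.1.3.1 also covers other unanticipated serious problems, so a UADE need not be an SAE.
- **That recurrences disappear from the report.** SAP 4.8.1 tabulates AEs that are not treatment-emergent and lists all AEs, so a recurrence would be reclassified.

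**Conclusion.** The TEAE window in SAP 4.8.1 is wrong as written, with modest impact. It runs 23 days beyond routine AE collection, and any events in those days are selected on relatedness, seriousness or device association. The tables should not be read as 30-day post-treatment incidence. The size in days is firm: it rests on a last dose at Day 29 and on the 7-day and 30-day rules, and visit windows leave at least 19 days without planned contact. The number of events affected cannot be derived from the documents; that it is small is a judgment from the narrow routes of entry.

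The recurrence problem holds only on the literal reading, only for events that resolved before dosing, and only when they return at the same or lower severity. Its consequence is misclassification between two reported tables, and it calls for clearer wording.

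**What to change.** In SAP 4.8.1, define a TEAE as any AE with onset on or after the first dose and through 7 days after the last dose, including recurrence of an event that resolved before dosing, or any pre-existing AE that worsens in that period. List SAEs and UADEs reported with later onset separately, labelled as outside the period of routine collection.

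On the nominal schedule the TEAE window then runs from Day 1 to Day 36 and leaves no days outside routine collection. Keeping 30 days would instead require collecting all AEs to Day 59, 23 days past the last planned contact.

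The cost is one SAP sentence and the matching table and listing specifications; no visit is added, and the 7-day collection rule in the protocol stays as it is. The downside is that a late related SAE moves from the TEAE table to a listing, so the safety text of the study report should point to that listing.

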4.8.2 Laboratory Data

Clinical laboratory values will be provided in standard international (SI) units by the central laboratory.

Summaries of laboratory data using descriptive statistics by study visit will be presented based on the SI units, including absolute results and changes from baseline. This includes serum chemistry, hematology, coagulation, urinalysis, and additional tests. In the event of repeat or unscheduled assessments, the last non-missing value per study day/time will be used in the summary statistics.

Shift analyses of laboratory data from baseline to post-baseline (day 15 and day 29, respectively) will be performed. Results for laboratory data will be presented by category (above normal limit, within normal limit, below normal limit). For shift tables, subjects who are missing either assessment will not be included in the percentage calculation (numerator or denominator).

All laboratory data, including repeated values and results from unscheduled visits, will be presented in data listings, with indication of higher or lower than the associated normal range of each laboratory test.

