## 6. STUDY PROCEDURES AND SCHEDULE

## **6.1.** Study Procedures

## **6.1.1.** Study Specific Procedures

The study-specific assessments are detailed in this section and outlined in Table 1. At Screening, any results falling outside of the reference ranges may be repeated 1 time at the discretion of the Investigator.

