#### 6.2.9. Unscheduled Visit

If the subject returns to the clinic for an unscheduled visit (eg, to follow-up on an abnormal laboratory test), the procedures performed at this visit will be recorded in the eCRF and source documentation.

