# 6.3. Vital Signs and Physical Examinations

A comprehensive physical examination (review of all body systems), height, weight, and vital signs assessment will be performed at Screening.

A comprehensive physical examination includes a review of the following systems: head/neck/thyroid, eyes/ears/nose/throat, respiratory, cardiovascular, lymph nodes, abdomen, skin, musculoskeletal, and neurological. Breast, anorectal, and genital examinations will be performed when medically indicated. After screening, any clinically significant abnormal findings in physical examinations should be reported as AEs.

Height and weight will be measured with shoes off. Height is to be measured using a wall mounted stadiometer.

Vital signs include orthostatic blood pressure (systolic and diastolic), temperature (oral), pulse rate, and respiratory rate. These will be assessed following a 5 minute rest (seated or supine). At visits when study drug is administered at the site, vital sign assessments will be collected before the dose of study drug and 1 hour after abaloparatide-sMTS application for blood pressure, pulse and respiratory rate. Seated or supine and standing blood pressure measurements will be performed at each visit during the Treatment Period. In addition, pulse rate will be collected 15 minutes after abaloparatide-sMTS application. Temperature will only be collected predose.

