## 6.4. 12-Lead Electrocardiogram

A standard, 12 lead ECG will be performed. Two hard copies of the ECG should be printed and signed by the Investigator at the site; the first copy will be kept in the subject's medical chart and the second copy will be kept in the study file for retrospective collection by the Sponsor, if necessary. Any abnormalities should be noted and clinical relevance should be documented. An ECG will be recorded immediately prior to dosing and at 1 hour after abaloparatide-sMTS application on Day 1 (Visit 3), Day 15 (Visit 4) and Day 29 (Visit 5). Additional ECGs may be performed as clinically indicated.

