Serum calcium, phosphorus and albumin will be measured predose from the standard chemistry panel on Day 1, Day 15 and Day 29, and from a separate blood draw at 4 hours after abaloparatide-sMTS application on Day 1, Day 15, and Day 29. Blood draw for cAMP will be done predose and 30 minutes after sMTS application at Day 1, Day 15 and Day 29.

In the event of medically significant, unexplained, or abnormal clinical laboratory test values, the test(s) should be repeated and followed up until the results have returned to within the normal range or an adequate explanation for the abnormality is found. Clinically significant changes in laboratory tests that occur during the course of the study are to be reported as AEs unless included as part of a reported diagnosis (see Section 7).

The clinical laboratory will clearly mark all laboratory test values that are outside the normal range and the Investigator will indicate the clinical relevance of these out of range values.

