4.8.3 Vital Signs

Vital signs data will be summarized by visit (and timepoint if applicable). Descriptive statistics will be provided for the observed value and the change from baseline values. If a subject has multiple results on the vital signs at a particular visit, the last non-missing value will be used for the summary.

All vital signs data will be presented for each subject in a data listing.

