4.8.4 Electrocardiogram

Descriptive statistics will be provided to summarize ECG parameters and changes from baseline by visit and time point. The ECG parameters include heart rate (bpm), RR interval (msec), PR interval (msec), QRS duration (msec), QT interval (msec), and QTcF (Fridericia) (msec). In the event of repeat or unscheduled assessments for a given time point, the last non-missing value for the time point will be used in the tabulations.

Descriptive statistics will be provided for the observed value and the change from pre-dose values by visit. The number (%) of subjects experiencing heart rate increase from pre-dose and the occurrence per subject will be summarized with various threshold values (ranging from >5 bpm to >40 bpm).

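### Keeping the last repeat can tilt by-visit laboratory summaries toward normal, because the protocol repeats laboratory tests when they are abnormal; the matching vital-signs rule is also keyed to the wrong unit

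*SAP*

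**What the plan says.** The SAP has three rules for multiple readings, each keyed to a different unit.

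- **Laboratory (SAP 4.8.2), by study day/time:** for repeat or unscheduled assessments, "the last non-missing value per study day/time will be used in the summary statistics".
- **Vital signs (SAP 4.8.3), by visit:** "If a subject has multiple results on the vital signs at a particular visit, the last non-missing value will be used for the summary".
- **ECG (SAP 4.8.4), by time point:** "the last non-missing value for the time point will be used in the tabulations".

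The protocol says when readings are repeated.

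- **Laboratory, on study (6.5.1):** for medically significant, unexplained or abnormal values, "the test(s) should be repeated and followed up until the results have returned to within the normal range". The sentence goes on to allow a second stopping point, an adequate explanation of the abnormality. Section 6.2.9 gives follow-up of an abnormal laboratory test as its example of an unscheduled visit.
- **Laboratory, at Screening (6.1.1):** "any results falling outside of the reference ranges may be repeated 1 time at the discretion of the Investigator".
- **ECG (6.4):** "Additional ECGs may be performed as clinically indicated".
- **Vital signs (6.3):** no trigger for a repeat is stated. Only planned readings are described: predose, 1 hour, seated or supine and standing pressures, and "In addition, pulse rate will be collected 15 minutes after abaloparatide-sMTS application".

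SAP 4.8.2 plans shift tables from baseline to Day 15 and to Day 29, with no value-selection rule of their own. Baseline is the last value before the first dose (SAP 3.4). Analyses use nominal visits without windows (SAP 3.11).

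**The concern.** If an abnormal result is the reason for a repeat and a normal result is one reason to stop, the last value in the series is not a neutral choice. Ordinary within-subject variation makes some repeats fall back inside the range although the subject has not changed. A last-value rule then moves those subjects from abnormal to normal, and no opposite rule moves anyone from normal to abnormal.

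Safety and tolerability is a stated secondary objective, and albumin-corrected calcium is also a secondary pharmacodynamic endpoint. All safety analyses are descriptive, so the tables are the safety result. No worst post-baseline or any-abnormality laboratory table is planned that would recover a replaced value.

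The vital-signs rule raises a separate wording problem. Each treatment visit has several planned readings, so a rule that keeps one value per visit would, read literally, remove planned data.

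**Working it through.** The documents give no figure on this point and no power calculation, so there is nothing to reproduce. The check has two parts.

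**1. Size of the laboratory effect.** The abnormal rates and correlations below are assumptions. Only the sample size of about 22 comes from the documents (protocol synopsis).

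Let *p* be the share of first readings that are abnormal, *f* the share of those repeated once at the same timepoint, and *J* the probability that both first reading and repeat are abnormal. With no true change between readings,

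reported rate = (1 − *f*)·*p* + *f*·*J*.

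*J* comes from a bivariate normal with a one-sided limit and correlation ρ between first reading and repeat.

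| *p* | ρ | *J*, the rate if all are repeated (*f* = 1) | Rate if half are repeated (*f* = 0.5) |
|---|---|---|---|
| 20% | 0.5 | 8.7% | 0.5 × 20 + 0.5 × 8.7 = 14.4% |
| 20% | 0.7 | 11.3% | 0.5 × 20 + 0.5 × 11.3 = 15.7% |
| 20% | 0.85 | 13.9% | 0.5 × 20 + 0.5 × 13.9 = 17.0% |
| 10% | 0.5 / 0.7 / 0.85 | 3.2 / 4.7 / 6.2% | 6.6 / 7.4 / 8.1% |

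In 22 subjects, 22 × 0.20 = 4.4 abnormal becomes 22 × 0.087 = 1.9 to 22 × 0.139 = 3.1 when all are repeated.

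A second simulation (1,000,000 draws per scenario) used a two-sided range of ±1.96 SD, a true on-drug shift of 1 SD, and ρ = 0.5 / 0.7 / 0.9:

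- First value: 17.0% out of range.
- Last value after one repeat of every abnormal: 6.9 / 9.1 / 12.4%.
- Half of the abnormals repeated: 11.9 / 13.0 / 14.7%.
- Up to three repeats until normal: 2.4 / 4.8 / 9.4%.
- Repeats unrelated to the result: 16.9 to 17.1%, so no drift.
- The mean falls by only 0.12 / 0.07 / 0.02 SD after one repeat, and by at most 0.18 SD after three.

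**2. The vital-signs wording against its neighbours.** SAP 4.8.3 first promises summaries by visit and, where applicable, timepoint, then selects one value per visit. SAP 4.8.3.1 counts orthostatic hypotension by visit and time point, which needs two positions at each time point. SAP 4.8.3.2 summarises pulse change from predose, which needs at least two readings per visit. None of these can be produced if one reading per visit survives. The ECG rule in SAP 4.8.4 avoids the problem by naming the time point.

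**The case against.** Several counter-arguments limit the point.

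- **Trigger.** The abnormal-result trigger is documented for laboratory tests only. A reader might infer that pulse, heart-rate and orthostatic counts drift toward normal as well. The documents do not support that: extra ECGs follow clinical indication, no trigger is given for repeating vital signs, and without selective repeats the rule causes no drift. For those data it is possible but not shown.
- **Reach.** The laboratory rule works per study day/time. A repeat at a later unscheduled visit has a different study day and, read literally, leaves the Day 15 or Day 29 value in place. This stands, but the SAP does not say how an unscheduled result maps to a nominal visit, so the reach is open rather than nil.
- **Shift tables.** A reader might take it as settled that these drift. The rule is worded for summary statistics, and the shift paragraph is silent. Baseline is itself a last predose value, so selection could act at both ends and the net direction of shifts is not established.
- **Stopping point.** Repeats end at a normal result or at an adequate explanation. This weakens the selection but does not remove it, since the trigger remains an abnormal result.
- **Planned vital signs.** A reader might infer that planned readings will be discarded. The adjoining analyses show that this cannot be intended. It is a wording conflict.
- **Visibility.** All laboratory values, repeats included, are listed with high and low flags, vital signs are listed, and clinically significant changes are reported as adverse events. With about 22 subjects the listings can be read in full. This confines the loss to the summary tables but does not correct the counts there.

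**Conclusion.** The point holds for laboratory data, conditionally. Where a repeat falls on the same study day/time, or is assigned to the same nominal visit, the by-visit summaries are selected toward normal, as are the shift tables if they use the same value. Counts out of range are affected materially and means little.

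The fall from 20% to about 9 to 14% is an illustrative upper bound for single repeats. It assumes that every abnormal value is repeated once at the same timepoint, that nothing truly changes, and that the correlation is 0.5 to 0.85. With half repeated the figure is about 14 to 17%. Repeating until normal would enlarge the effect, and repeats made without regard to the result would remove it. The documents do not say how often same-timepoint repeats will occur.

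Separately, the unit in SAP 4.8.3 is inconsistent with the analyses around it and needs rewording whether or not anything is repeated.

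**What to change.** 1. In SAP 4.8.2, 4.8.3 and 4.8.4, use the first valid scheduled value at each time point for by-visit summaries. Use a repeat only when the scheduled value is missing or documented as technically invalid.
2. State that the Day 15 and Day 29 shift tables use the same value, and say how unscheduled results are assigned to nominal visits. Reconcile the starting point of the shifts at the same time: protocol 8.4.4 takes them from the Screening visit, the SAP from baseline.
3. Add a supplementary worst post-baseline abnormality table that includes repeat and unscheduled results. It should sit beside the planned shift tables, not replace them, with a note that worst-value counts rise with the number of readings taken.
4. Reword the rule in SAP 4.8.3 so that it applies to a given time point and position.

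The cost is SAP wording, minor programming and one extra table. The reported abnormality counts may be slightly less favourable.
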